22.3 Appendix 3 – Liver Safety

Monthly monitoring of liver chemistry will occur during the study treatment period. The following should occur if a subject meets any of the liver chemistry stopping criteria as outlined in Section 6.4.5 of [000] of the protocol:

- Subject should immediately be withdrawn from treatment. Do not re-challenge with study treatment.
- Completed the “Safety Follow-up Procedures” listed below.
- Upon completion of the safety follow-up, the subject must be withdrawn from the study unless further follow-up is required.

Subjects with ALT > 3x ULN and bilirubin > 2x ULN (> 35% direct); or ALT > 3x ULN and INR > 1.5:

- **This event is an SAE** and should be reported using the SAE Reporting Form (reference [Section 11.2](#)). Serum bilirubin fractionation should be performed, if testing is available. If fractionation is unavailable, urinary bilirubin is to be measured via dipstick (a measurement of direct bilirubin, which would suggest liver injury).

Note: INR testing is not required per protocol and the threshold value does not apply to subjects receiving anticoagulants.

- Make every reasonable attempt to have the subject return to the clinic within 24 hours for repeat liver chemistries, additional testing and close monitoring (with specialist or hepatology consultation recommended).
- Monitor the subject twice weekly until liver chemistries (ALT, AST, alkaline phosphatase, bilirubin) resolve, stabilize or return to within baseline values.

Subjects with ALT > 5x ULN or ALT > 3x ULN who have hepatitis symptoms or rash, cannot be monitored for 4 weeks or have elevations that persist ≥ 4 weeks:

- Make every reasonable attempt to have the subject return to the clinic within 24-72 hours for repeat liver chemistries and additional testing.
- Monitor subject weekly until liver chemistries (ALT, AST, alkaline phosphatase, bilirubin) resolve, stabilize or return to within baseline values.

Subjects with ALT > 3x ULN and < 5x ULN and bilirubin < 2x ULN, who do not exhibit hepatitis symptoms or rash:

- Subject may continue study treatment, if liver chemistries (ALT, AST, alkaline phosphatase, bilirubin) can be monitored weekly for up to 4 weeks.

- If the subject later meets the liver chemistry stopping criteria (outlined in Section 6.4.5 of the protocol), immediately withdraw study treatment, perform additional testing and continue safety follow-up until liver chemistries resolve, stabilize or return to baseline values.
- After 4 weeks of monitoring, if ALT < 3x ULN and bilirubin < 2x ULN, subject must be monitored twice monthly until liver chemistries normalize or return to within baseline values.

Additional follow-up procedures for subjects who meet any of the liver safety stopping criteria:

- Viral hepatitis serology including:
 - Hepatitis A Immunoglobulin M (IgM) antibody,
 - Hepatitis B surface antigen and Hepatitis B Core Antibody (IgM),
 - Hepatitis C RNA,
 - Cytomegalovirus IgM antibody,
 - Epstein-Barr viral capsid antigen IgM antibody (or if unavailable, obtain heterophile antibody or monospot testing), and
 - Hepatitis E IgM antibody.
- Blood sample for PK analysis, obtained within 48 hours of last dose. Record the date/time of the PK blood sample draw and the date/time of the last dose of study treatment prior to blood sample draw in the eCRF. If the date or time of the last dose is unclear, provide the subject's best approximation. If the date/time of the last dose cannot be approximated or a PK sample cannot be collected in the time period indicated above, do not obtain a PK sample. Instructions for sample handling and shipping are outlined in the laboratory manual.
- Serum creatine phosphokinase and lactate dehydrogenase.
- Fractionate bilirubin, if total bilirubin > 2x ULN.
- Assess eosinophilia.
- Record the appearance or worsening of clinical symptoms of hepatitis (fatigue, nausea, vomiting, right upper quadrant pain or tenderness, fever, rash or eosinophilia) as relevant on the AE eCRF.

- Record use of concomitant medications, acetaminophen, herbal remedies, other over the counter medications, or putative hepatotoxins on the Concomitant Medications eCRF.
- Record alcohol use in the eCRF.
- **In addition, the following are required for subjects with ALT > 3x ULN and bilirubin > 2x ULN (< 35% direct) but optional for other abnormal liver chemistries:**
 - Anti-nuclear antibody, anti-smooth muscle antibody, Type 1 anti-liver kidney microsomal antibodies and quantitative total immunoglobulin G (IgG or gamma globulins).
 - Serum acetaminophen adduct HPLC assay (quantifies potential acetaminophen contribution to liver injury in subjects with definite or likely acetaminophen use in the preceding week [[James 2009](#)]).
 - Liver imaging (ultrasound, MRI, or CT) to evaluate liver disease. Data should be entered into the eCRF, if these tests are performed.

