Once subjects are engaged in care at the treatment clinic, they will continue to receive SUBLOCADE for 6 months. The second 300 mg injection will be administered on Day 8 (-0/+4 days) after the first injection, with subsequent 300 mg injections administered at 28-day (-2/+4 days) intervals over approximately 6 months for a total of 7 injections. If necessary, for tolerability, the dose of SUBLOCADE can be reduced to 100 mg. All subjects will receive site standard psychosocial therapy at least weekly during the first 3 months of treatment, and twice monthly thereafter if clinically stable.

All subjects will complete an End of Treatment (EOT) / Early Termination (ET) visit 28 days after their last injection of SUBLOCADE. Within 3 months prior to or at the EOT visit, the Investigator or a medically qualified sub-investigator will discuss the subject's available treatment options and arrange referral. All subjects will receive a safety follow-up telephone call, 30 days after their EOT/ET visit to assess AEs, SAEs, pregnancy status (if applicable) and concomitant medications. Subjects who decline to continue in medication assisted treatment (MAT) will receive monthly safety follow-up phone calls for an additional 5 months (6 months total) to assess SAEs, pregnancy status (if applicable) and concomitant medications.

Primary Endpoint(s):

The primary endpoint of this study is:

- Time to repeat OD or opioid-related death. Repeat OD or opioid-related death will be measured from electronic medical records and state death registries.
- Additional comparisons on repeat OD and death rates will be made to concurrent patients who decline to participate in the SUBLOCADE injection.

Secondary Endpoint(s):

The key secondary endpoint of the study is:

- Treatment engagement as measured by attending the outpatient clinic and receiving subsequent buprenorphine treatment at 3 and 6 months.

The secondary endpoints of this study are:

- Numbers and percent of subjects in treatment at 3 and 6 months after opioid OD.

Exploratory Endpoints:

The exploratory endpoints of this study are:

- Opioid craving in subjects as measured by Craving Visual Analog Scale (VAS) scores.
- Illicit opioid use as measured by urine drug screen (UDS) results.
- Genetic predictors of treatment response and OD.

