6.4.5 Liver Chemistry Stopping Criteria

Liver chemistry stopping criteria 1-5 are defined below:

1. The subject has ALT or AST $>3 \times$ ULN **and** bilirubin $>2 \times$ ULN ($>35\%$ direct bilirubin) (or ALT or AST $>3 \times$ ULN **and** international normalized ratio (INR) >1.5 , if INR measured).
Note: if serum bilirubin fractionation is not immediately available, withdraw study drug for that subject if ALT or AST $>3 \times$ ULN and bilirubin $>2 \times$ ULN. Serum bilirubin fractionation should be performed if testing is available. If testing is unavailable, the presence of detectable urinary bilirubin on dipstick should be recorded, indicating direct bilirubin elevations and suggesting liver injury.
2. The subject has ALT or AST $>8 \times$ ULN.
3. The subject has ALT or AST $>5 \times$ ULN but $<8 \times$ ULN persisting for > 2 weeks.

4. The subject has ALT or AST >3 x ULN if associated with symptoms (new or worsening) believed to be related to hepatitis (such as fatigue, nausea, vomiting, right upper quadrant pain or tenderness or jaundice) or hypersensitivity (such as fever, rash, or eosinophilia).
5. The subject has ALT or AST >5 x ULN but <8 x ULN and cannot be monitored weekly for >2 weeks.

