8 DESCRIPTION OF STUDY PROCEDURES

Study assessments and procedures, including the timing of assessments, are summarized in Appendix 1 and Appendix 2. Further details on efficacy assessments are provided in Section 8.6.

A signed written informed consent form must be obtained from the subject before any study assessments or procedures may be performed. At screening, if an assessment or procedure has already been performed as part of routine standard of care and was completed within the protocol-specific screening window, the assessment or procedure does not need to be repeated, unless clinically indicated. All assessments and procedures may be performed more frequently, if clinically indicated.

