8.5 Clinical Laboratory Tests

Clinical laboratory tests will be performed at the time points listed in the Schedule of Events ([Appendix 1](#) and [Appendix 2](#)) in a licensed clinical laboratory. Urine pregnancy tests and urine drug screens may be performed using a licensed point of care test (dipstick). Abnormal liver function tests (LFTs) will be followed at clinic visits according to investigator's judgement. An etiological evaluation will be performed if a hepatic adverse event (AE) is suspected.

Subjects are to be in a seated or supine position during blood collection.

The following clinical laboratory tests specified in Table 1 will be performed.

Table 1 List of Laboratory Tests

Hematology:	Serum Chemistry:
Hematocrit	Albumin
Hemoglobin	Alkaline phosphatase
Mean corpuscular hemoglobin	Alanine aminotransferase (ALT)
Mean corpuscular hemoglobin concentration	Amylase
Mean corpuscular volume	Aspartate aminotransferase (AST)
Platelet count	Blood urea nitrogen
Red blood cell count	Calcium
White blood cell count with 3-part differential	Calculated creatinine clearance
	Carbon dioxide
Pregnancy:	Chloride
Urine Pregnancy (only for females not postmenopausal or surgically sterile for at least 1 year)	Creatinine
	Creatine kinase and subtypes
	Gamma-glutamyl transferase
	Globulin
Additional Tests:	Glucose (non-fasting)
HIV	Lactate dehydrogenase
HCV B/C	Magnesium
Urine Drug Screen (UDS):	Phosphorus
Opioids	Potassium
Fentanyl	Sodium
Buprenorphine	Total bilirubin
Methadone	Direct bilirubin
Oxycodone	Total cholesterol
Amphetamines	Total protein
Cannabinoids	
Barbiturates	
Benzodiazepines	
Cocaine	
Methamphetamines	
Phencyclidine	
Breath alcohol test	

HIV = human immunodeficiency virus antibodies; HCB = Hepatitis B Virus; HCV = Hepatitis C virus.

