Procedure / Assessment	Treatment Period									
	Visit 2	Visit 3	Visit 4	Visit 5	Visit 6	Visit 7	Visit 8	Visit 9	Visit 10	Visit 11
	Wk 1 D 2 (-0/+3) D	Wk 2 D 8 (-0/+4) D	Wk 3 D 15 ±4 D	Wk 4 D22 (±4) D	Wk 5 D29 (±4) D	Wk 6 D36 (-2/+4) D	Wk 7 D43 (±4) D	Wk 8 D50 (±4) D	Wk 9 D57 (±4) D	Wk 10 D64 (-2/+4) D
Counselling	X	X	X	X	X	X	X	X	X	X
Urine Drug Screen	X	X	X	X	X	X	X	X	X	X
COWS	X	X	X	X	X	X	X	X	X	X
MINI International Neuropsychiatric Interview	X									
Delay Discounting Task	X									
Opioid Demand Task	X									
OC-VAS ^a	X	X	X	X	X	X	X	X	X	X
TEA	X		X							
HCRUQ	X		X				X			
MSQ	X		X							
WPAI:SHP	X									
AE Assessment	X	X	X	X	X	X	X	X	X	X
Concomitant Medications Assessment	X	X	X	X	X	X	X	X	X	X
Brief Physical Examination	X									
Vital Signs	X	X	X	X	X	X	X	X	X	X
Urine Pregnancy Test ^b	X	X	X	X	X	X	X	X	X	X
SUBLOCADE Injection		X				X				X
Liver function lab tests	X				X				X	
Laboratory Tests	X									

HCRUQ = Health Care Resource Utilization Questionnaire; WPAI:SHP = Work Productivity and Activity Impairment Questionnaire: Specific Health Problem

- a. OC-VAS will be assessed prior to SUBLOCADE injection
- b. Urine pregnancy test, only for females of child-bearing potential. Results will be obtained prior to SUBLOCADE injection.

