Appendix 2 - Treatment Clinic Schedule of Events – (Week 1 Day 2 – Week 25 Day 169)

Procedure / Assessment	Treatment Period									30-Day Safety Follow-up Telephone Call ^d
	Visit 12	Visit 13	Visit 14	Visit 15	Visit 16	Visit 17	Visit 18	Visit 19	End of Treatment / Early Term	
	Wk 11 D 71 (±4) D	Wk 12 D 78 (±4) D	Wk 13 D 85 (±4) D	Wk 14 D92 (-2/+4) D	Wk 16 D106 (±4) D	Wk 18 D120 (-2/+4 D	Wk 20 D134 (±4) D	Wk 22 D148 (-2/+4) D	Wk 25 D 169 (±4) D	Wk 29 Day 199 (±4) D
Counselling	X	X	X	X	X	X	X	X	X	
Urine Drug Screen	X	X	X	X	X	X	X	X	X	
Delay Discounting Task		X							X	
Opioid Demand Task		X							X	
OC-VAS ^a	X	X	X	X	X	X	X	X	X	
COWS	X	X	X	X	X	X	X	X	X	
TEA	X					X			X	
HCRUQ	X			X		X		X	X	
MSQ	X					X			X	
Employment Question	X					X			X	X footnote
AE Assessment	X	X	X	X	X	X	X	X	X	X
Concomitant Medications Assessment	X	X	X	X	X	X	X	X	X	
Vital Signs	X	X	X	X	X	X	X	X	X	
Urine Pregnancy Test ^b	X	X	X	X	X	X	X	X	X	X
SUBLOCADE Injection				X		X		X		
Liver function laboratory testing			X				X		X	

- OC-VAS will be assessed prior to SUBLOCADE injection
- Urine pregnancy test, only for females of child-bearing potential. Results will be obtained prior to SUBLOCADE injection.
- All subjects will receive a safety follow-up telephone call 30 days after their EOT/ET visit to assess AEs, SAEs, pregnancy status (if applicable) and concomitant medications. Subjects who decline to continue in MAT will receive monthly safety follow-up phone calls for an additional 5 months (6 months total) to assess SAEs, pregnancy status (if applicable) and concomitant medications.

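### Appendix 3 promises monthly liver monitoring, but Appendix 2 leaves late intervals of 49 and 35 days, and the Day 120 injection falls 35 days after the last scheduled liver test.

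*Combined protocol and SAP*

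**What the plan says.** Appendix 3 (Liver Safety) sets the rule without qualification: "Monthly monitoring of liver chemistry will occur during the study treatment period".

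Section 8.5 sends sites to a table for the timing: "Clinical laboratory tests will be performed at the time points listed in the Schedule of Events". In that table (Appendix 2), the row "Liver function lab tests" is marked at Visits 2, 6 and 10 (Days 2, 29 and 57). On the continuation page, the row "Liver function laboratory testing" is marked at Visit 14 (Day 85), Visit 18 (Day 134) and End of Treatment (Day 169). Visits 15, 16, 17 and 19 have no liver test. After Day 1, injections are marked on Days 8, 36, 64, 92, 120 and 148.

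Two provisions allow more testing. Section 8 says "All assessments and procedures may be performed more frequently, if clinically indicated". Section 8.5 says "Abnormal liver function tests (LFTs) will be followed at clinic visits according to investigator's judgement". Neither adds a scheduled test.

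**The concern.** A site that follows Appendix 2 exactly will break the monthly rule in Appendix 3 from Day 85 onward. The early part of the schedule shows what monthly means in this protocol: tests about 28 days apart, each roughly a week before an injection. That pattern stops after Day 85.

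Four of the five stopping criteria in Section 6.4.5 can be met by a subject with no symptoms. Criterion 2 is ALT or AST above 8 times ULN. Criterion 3 is a value between 5 and 8 times ULN, "ULN persisting for > 2 weeks". Criterion 1 combines raised transaminases with raised bilirubin or INR, and criterion 5 concerns the same range as criterion 3 when weekly monitoring is not possible. Only criterion 4 depends on symptoms. For the others, AE questioning at visits does not replace a measurement. Section 1.1.3 lists raised hepatic enzymes among the reactions seen in at least 5% of subjects, so the effect being monitored is a known one.

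A subject who develops a silent elevation after Day 85 would receive the Day 120 injection, a month-long depot, with no scheduled liver result since before the Day 92 injection.

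**Working it through.** **Inputs (Appendix 2).** Liver test days and windows: 2 (-0/+3), 29 (±4), 57 (±4), 85 (±4), 134 (±4), 169 (±4). Injection days and windows after Day 1: 8 (-0/+4), then 36, 64, 92, 120 and 148 (each -2/+4).

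**Formulas.** Nominal interval = later day − earlier day. Shortest = earliest permitted later day − latest permitted earlier day. Longest = latest permitted later day − earliest permitted earlier day.

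**Intervals between liver tests**

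| From – to | Nominal | With windows |
|---|---|---|
| 2 – 29 | 27 | 20–31 |
| 29 – 57 | 28 | 20–36 |
| 57 – 85 | 28 | 20–36 |
| 85 – 134 | 49 | 130 − 89 = 41 to 138 − 81 = 57 |
| 134 – 169 | 35 | 165 − 138 = 27 to 173 − 130 = 43 |

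The stated monthly frequency is reproduced for the first three intervals and not for the last two.

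**Lag from last scheduled liver test to injection**

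| Injection | Last test | Nominal lag | With windows |
|---|---|---|---|
| Day 8 | Day 2 | 6 | 3–10 |
| Day 36 | Day 29 | 7 | 1–15 |
| Day 64 | Day 57 | 7 | 1–15 |
| Day 92 | Day 85 | 7 | 1–15 |
| Day 120 | Day 85 | 35 | 118 − 89 = 29 to 124 − 81 = 43 |
| Day 148 | Day 134 | 14 | 8–22 |

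Only Day 120 is out of line. The Day 85 window closes on Day 89 and the Day 92 window opens on Day 90, so the last scheduled result before the Day 120 injection always predates the Day 92 injection as well.

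**Depot removal.** Section 6.4.5.1 allows surgical removal within 14 days of injection. The next test after Day 120 is on Day 134, nominally 14 days later and 6 to 20 days with windows (130 − 124 to 138 − 118). An elevation already present on Day 120 could be found too late for removal.

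**Sensitivity to End of Treatment timing.** The synopsis places that "visit 28 days after their last injection of SUBLOCADE". With the last injection on Day 148 this is Day 176, against Day 169 in Appendix 2. The final interval would then be 176 − 134 = 42 days.

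**What spacing is achievable.** Existing visits between the Day 85 and Day 169 tests are on Days 92, 106, 120, 134 and 148. The smallest achievable longest interval is:
- one test: 49 days (Day 134 gives 49 and 35; Day 120 gives 35 and 49);
- two tests: 35 days (for example Days 106 and 134 give 21, 28 and 35);
- three tests: 28 days.

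Moving the Day 134 test therefore cannot repair the schedule. With Day 134 kept, the only pair of added visits that brings the maximum to 28 is Days 106 and 148:
- 106 − 85 = 21 (13–29)
- 134 − 106 = 28 (20–36)
- 148 − 134 = 14 (8–22)
- 169 − 148 = 21 (13–27)

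The Day 120 lag becomes 120 − 106 = 14 days (8–22). If End of Treatment is on Day 176, the last interval becomes 176 − 148 = 28 days.

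**The case against.** The strongest reply is that the documents set no maximum gap. Counting in 28-day study months, months 1 to 5 each contain a scheduled test, and End of Treatment on Day 169 closes month 6. On that count, however, nominal Days 141 to 168 have no test. On 30-day months, Days 91 to 120 have none. Neither count gives a test in every month, and a gap of at least 41 days is hard to call monthly.

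Several points do stand in part. The 35-day interval is weak evidence by itself, because its windows run from 27 to 43 days and the early schedule already tolerates 36. No section requires a liver result within a set time before an injection, so the lag to Day 120 measures the consequence and is not a second broken rule. The exposure is narrow: symptomatic subjects are picked up by AE assessment and clinically indicated testing, and Appendix 3 provides closer follow-up of known elevations. The wider spacing may also be deliberate, since counselling and visits become less frequent after month 3.

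If it is deliberate, Appendix 3 should say so. Rewording Appendix 3 to defer to the table would remove the inconsistency at no burden, but it would withdraw a stated safety rule instead of delivering it.

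**Conclusion.** The concern holds. The firm breach is the 49-day interval from Day 85 to Day 134, which is at least 41 days under any permitted visit timing, against 27 to 28 days earlier in the same schedule. The 35-day final interval is a lesser departure on the Appendix 2 timing and becomes 42 days on the synopsis timing for End of Treatment. The consequence for dosing is limited to the Day 120 injection. The subjects at risk are those with a new, asymptomatic elevation after Day 85; the documents give no figure for how many that would be. There is no effect on the efficacy analysis or power.

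This rests on reading monthly as about 28 to 31 days and on the Appendix 2 marks sitting in the columns they appear to occupy. The rows fill the expected number of columns and the later injection marks fall on visits with the -2/+4 window, so a table-reading error is unlikely. The point should be corrected.

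**What to change.** Keep the existing tests and add a liver function panel in Appendix 2 at Visit 16 (Day 106) and Visit 19 (Day 148). The longest interval with windows is then 36 days, the same as the early intervals already allow.

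If only one panel is acceptable, add Visit 16. That gives late intervals of 21, 28 and 35 days and protects the Day 120 injection, but leaves the softer 35-day interval. The End of Treatment day should be reconciled between the synopsis and Appendix 2 in the same amendment, because the final interval depends on it.

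The cost is an edit to one row of Appendix 2 and two extra routine panels per subject, at most 2 × 100 = 200 if all subjects are retained, at visits already scheduled. The burden is two additional blood draws per subject, in a population where Appendix 1 (footnote d) already anticipates that research blood cannot always be obtained.

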6.4.5.1 Study Treatment Re-challenge

Study treatment re-challenge after liver chemistry stopping criteria are met by any study subject is not allowed. If clinically indicated, the SUBLOCADE depot may be surgically removed within 14 days of the injection.

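### A liver stopping criterion first met at a scheduled test after Visit 2 comes too late for the Appendix 3 PK sample, which is barred once 48 hours have passed since the injection

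*Combined protocol and SAP*

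**What the plan says.** Appendix 3 (Section 22.3) lists follow-up procedures for subjects who meet a liver stopping criterion. One is a "Blood sample for PK analysis, obtained within 48 hours of last dose". The same item closes the window firmly: where "a PK sample cannot be collected in the time period indicated above, do not obtain a PK sample".

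Section 6.4.5.1 forbids re-challenge after a criterion is met and adds that, when clinically indicated, "the SUBLOCADE depot may be surgically removed within 14 days of the injection".

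The Synopsis (Study Design) sets the dosing calendar: "The second 300 mg injection will be administered on Day 8 (-0/+4 days) after the first injection", with later ones at "28-day (-2/+4 days) intervals over approximately 6 months for a total of 7 injections". Appendix 3 states "Monthly monitoring of liver chemistry will occur during the study treatment period", and Appendix 2 fixes the days in its rows "Liver function lab tests" (first part) and "Liver function laboratory testing" (second part).

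Two other sections bear on the point. Section 1.1.1 describes a product that releases buprenorphine over about a month. Section 9.3.1 requires the time of every injection to be entered in the eCRF.

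**The concern.** The PK sample is triggered by a liver result, but its time limit runs from the injection. Whether the sample can be taken therefore depends on how soon after a dose the liver test is done. If the calendar puts routine tests well beyond 48 hours, the rule does more than leave the sample optional: it forbids the sample in the subjects whose signal routine monitoring finds. The only planned drug-concentration measurement in a subject with a liver signal would then be lost by wording, at a time when a one-month depot is still releasing drug.

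The depot-removal window raises the same timing question over a longer span. If a test normally comes after day 14, scheduled monitoring seldom leaves that option open. Neither matter touches the primary endpoint. Both concern what can be done and learned once a liver signal appears.

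**Working it through.** **Inputs.** Injections: Appendix 1 (Day 1) and Appendix 2 (Visits 3, 7, 11, 15, 17 and 19). Liver tests: Appendix 2 (Visits 2, 6, 10, 14, 18 and EOT/ET). Windows: Appendix 2, namely Visit 2 -0/+3; Visit 3 -0/+4; later injection visits -2/+4; other liver-test visits ±4 days. They are taken around the scheduled days, as Section 1.1.2 also describes for dosing.

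**Reproducing the plan's figure.** Injection days are 1, 8 and 8 + 28k for k = 1 to 5: Days 1, 8, 36, 64, 92, 120 and 148. That is 7 injections, as the Synopsis states, on the days marked in Appendix 2.

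**Gap from injection to test.** Nominal gap = test day - last preceding injection day. Shortest gap = earliest test day - latest injection day. Longest gap = latest test day - earliest injection day.

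| Test | Last injection | Nominal gap (days) | Shortest | Longest |
|---|---|---|---|---|
| Visit 2, Day 2 | Day 1 | 2 - 1 = 1 | 2 - 1 = 1 | 5 - 1 = 4 |
| Visit 6, Day 29 | Day 8 | 29 - 8 = 21 | 25 - 12 = 13 | 33 - 8 = 25 |
| Visit 10, Day 57 | Day 36 | 57 - 36 = 21 | 53 - 40 = 13 | 61 - 34 = 27 |
| Visit 14, Day 85 | Day 64 | 85 - 64 = 21 | 81 - 68 = 13 | 89 - 62 = 27 |
| Visit 18, Day 134 | Day 120 | 134 - 120 = 14 | 130 - 124 = 6 | 138 - 118 = 20 |
| EOT, Day 169 | Day 148 | 169 - 148 = 21 | 165 - 152 = 13 | 173 - 146 = 27 |

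The EOT row uses Appendix 2. The Synopsis instead places EOT/ET 28 days after the last injection (148 + 28 = Day 176), which would lengthen that gap.

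**48-hour PK limit.** After Visit 2 the shortest gap under any permitted combination is 6 days. All five tests miss the limit. Visit 2 can meet it if the draw is on Day 2 or 3. Even then the result must come back and the subject return before 48 hours have passed, and Appendix 3 allows 24 hours, or 24 to 72 hours, for the return.

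**14-day removal window.** At nominal timing, four of the five tests (Days 29, 57, 85 and 169) come 21 - 14 = 7 days after it closes. Day 134 falls on day 14 itself. Laboratory turnaround is not stated; any turnaround of a day or more closes the window at nominal Day 134 too. Counting permitted day combinations (not probabilities), a gap of 14 days or less occurs in 42 of 63 at Day 134, in 3 of 45 at Day 29, and in 3 of 63 at each of Days 57, 85 and 169. The first test after injection 5 (Day 92) is 134 - 92 = 42 days later, after injection 6 has been scheduled.

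**The case against.** A reader might infer that the PK sample can never be taken. The documents do not support that. Section 8 allows extra assessments when clinically indicated, and Visit 2 can fall within 48 hours. Appendix 3 also lets subjects with ALT between 3 and 5 times ULN, bilirubin below 2 times ULN and no hepatitis symptoms or rash stay on treatment with weekly tests for up to 4 weeks. A raised Day 29 result could lead to a draw on Day 36, an injection day, and a criterion found then could still meet the limit if the result is prompt.

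A reader might also infer that signals without symptoms can never be found inside the removal window. That fails for the same reason: the weekly monitoring is for subjects without symptoms, and a Day 43 draw is 7 days after the Day 36 injection. The Day 134 test can also fall inside 14 days.

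Nor does the calendar contradict Section 6.4.5.1. Removal there is permitted, not required, and no link to scheduled tests is promised. Omitting a late PK sample likewise breaks no rule, because the text provides for it. The documents do not state what the sample is for, and sample handling is left to a laboratory manual that is not part of them. Finally, not every criterion in Section 6.4.5 arises at a single test: criterion 3 needs persistence beyond 2 weeks and criterion 4 needs symptoms.

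All of this stands and limits the scope. It does not remove the finding that the PK item is empty for any criterion first met at one of the five scheduled tests. The documents give no reason why a sample after 48 hours would be uninformative for a depot of this kind.

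**Conclusion.** The point holds for liver stopping criteria first met at a scheduled test after Visit 2. There the last injection was nominally 21, 21, 21, 14 and 21 days earlier, 6 to 27 days across the windows, so the Appendix 3 sample is excluded at all five. It remains possible only around Visit 2, or when weekly or clinically indicated tests coincide with an injection visit.

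The depot-removal timing is secondary and weaker. The window has nominally closed at four of the five tests and is on its last day at the fifth, but the provision is optional and some permitted timings fall inside it. It calls for reconciliation, not for a finding of error.

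The result rests on the Appendix 2 days and windows and on reading the last dose as the last injection. The conclusion on the PK sample does not depend on laboratory turnaround or on which EOT day applies. How many subjects would be affected cannot be derived from the documents.

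**What to change.** **PK sample.** Reconcile the Appendix 3 sampling window with the Appendix 2 calendar and the monthly depot. One way is to allow the sample at the follow-up blood draw that Appendix 3 already requires, with the time since the last injection recorded, instead of barring it after 48 hours. The laboratory manual should be checked for consistency. The cost is protocol wording and at most one extra tube in a few subjects.

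**Depot-removal window.** The sponsor should reconcile Section 6.4.5.1 with Appendix 2, or state that scheduled monitoring is not meant to support removal. No clinical rule and no re-timing of draws is proposed here. Moving draws is a trade-off: Days 29, 57 and 85 now come 7 days before the next injection (36 - 29, 64 - 57, 92 - 85), so earlier draws would make the results available before that injection older. Stating the intent costs wording only.

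The EOT day (Day 169 in Appendix 2, 28 days after the last injection in the Synopsis) should be settled in the same edit.

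### Appendix 3 makes three liver work-up tests mandatory at under 35% direct bilirubin, the reverse of Section 6.4.5 and its own SAE tier; its tiers also name ALT only

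*Combined protocol and SAP*

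**What the plan says.** Section 6.4.5 gives five liver stopping criteria, each written for ALT or AST. Criterion 1 combines a transaminase above 3x ULN with bilirubin above 2x ULN and more than 35% direct, or with INR above 1.5 if measured. Its note treats bilirubin on a urine dipstick as "indicating direct bilirubin elevations and suggesting liver injury".

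Appendix 3 sets out what follows. Its opening rule applies "if a subject meets any of the liver chemistry stopping criteria as outlined in Section 6.4.5". Three tiers come next:

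- Tier 1: "Subjects with ALT > 3x ULN and bilirubin > 2x ULN (> 35% direct", or ALT above 3x ULN with INR above 1.5. This is declared an SAE, with 24-hour recall and twice-weekly chemistries. It describes the dipstick as "a measurement of direct bilirubin, which would suggest liver injury".
- Tier 2: "Subjects with ALT > 5x ULN or ALT > 3x ULN who have hepatitis symptoms or rash", with recall in 24 to 72 hours and weekly chemistries.
- Tier 3: "Subjects with ALT > 3x ULN and < 5x ULN and bilirubin < 2x ULN", without symptoms. Treatment may go on if weekly testing for up to 4 weeks is possible. A step-down line after those 4 weeks also uses ALT.

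A base list is headed "Additional follow-up procedures for subjects who meet any of the liver safety stopping criteria". At its end come the three extra items, with the trigger "the following are required for subjects with ALT > 3x ULN and bilirubin > 2x ULN (< 35% direct".

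Section 11 defines two kinds of potential Hy's Law case, both for ALT or AST, and sends them to Appendix 3 for management. Section 10.1.4 also points there for raised liver tests.

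**The concern.** Both places that explain the direct fraction treat it as the sign of liver injury. The extra work-up should therefore attach to the high-direct group, yet the printed sign attaches it to the low-direct group. A site following the text has no obligation to run the three tests where the evidence of injury is strongest.

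The tests bear on cause. Section 11 makes the first kind of potential Hy's Law case depend on finding no other explanation. Acetaminophen is a plausible one in this trial, because the Synopsis has subjects told at Visit 1 discharge that they may take it as needed, and the first clinic liver test is on Day 2 (window -0/+3).

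The ALT-only wording is a separate mismatch. Section 11 sends AST cases to an appendix whose tiers do not mention AST as a trigger.

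**Working it through.** No sample size or error rate is involved, so the check compares the texts and traces cases through them.

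**Thresholds side by side**

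| Place | Transaminase | Direct fraction |
|---|---|---|
| 6.4.5, criterion 1 | ALT or AST | > 35% |
| Appendix 3, tier 1 | ALT | > 35% |
| Appendix 3, extra work-up line | ALT | < 35% |
| 6.4.5, criteria 2 to 5 | ALT or AST | none |
| Section 11, both definitions | ALT or AST | none |
| Appendix 3, tiers 2 and 3 and step-down line | ALT | none |

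**Case A: ALT above 3x, bilirubin above 2x, confirmed above 35% direct.** Criterion 1 is met, so treatment stops. Tier 1 applies and the base list applies. The extra work-up line does not match, so 3 of its 3 items are optional.

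**Case B: the same, but below 35% direct.** Once bilirubin is fractionated, the bilirubin limb of criterion 1 is not met. This subject reaches the list only through criteria 2 to 5, the INR limb, or the note for when fractionation is not immediately available. For this subject the 3 items are mandatory. Nothing in the documents explains why B should be examined more than A.

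**AST coverage.** Seven lines of Appendix 3 depend on a transaminase threshold. Two cover AST by referring to the stopping criteria: the opening rule and the base-list heading. The other 7 - 2 = 5 name ALT only: three tiers, the step-down line and the extra work-up line. By contrast, 5 of 5 criteria in 6.4.5 and 2 of 2 definitions in Section 11 say ALT or AST.

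**Case C: AST-only, a stopping criterion met.** Treatment stops and the base list applies. No tier expressly gives a recall time or monitoring frequency, and the extra work-up line does not match.

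**Case D: AST-only, 3 to 5x ULN, no symptoms, bilirubin below 2x, INR not raised.** No stopping criterion and no tier applies. Section 8.5 has abnormal liver tests followed at clinic visits as the investigator judges. From Appendix 2, visits from Day 8 to Day 92 are 7 days apart. Days 92, 106, 120, 134 and 148 are 14 days apart, and Day 148 to Day 169 is 21 days. An ALT rise of the same size must be tested weekly for up to 4 weeks if treatment is to go on.

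**The case against.** The strongest reply is that the consequences are limited, and most of it stands.

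- A reader might infer that cases above 35% direct go uninvestigated. They do not. Tier 1 calls for further testing and recommends specialist input. The base list includes viral serology and a record of acetaminophen use. Section 8.5 and the Appendix 1 footnote on liver tests require an evaluation for cause whenever a hepatic adverse event is suspected. None of these names the three tests, so the reversed sign still matters.
- A reader might infer that AST-only Hy's Law cases have no management path. Section 11 sends them to Appendix 3, and its two definitions correspond roughly to tiers 1 and 2, so they can be read in. For AST of 5 to 8x, criterion 5 presupposes weekly monitoring. The gap is one of explicit wording, and it is clearest in Case D.
- A reader might set the scheduled liver tests (Days 2, 29, 57, 85, 134 and 169, so 27 to 49 days apart) against weekly testing. That overstates the difference, because abnormal results are followed at the more frequent clinic visits and Section 8 allows extra assessments when clinically indicated.
- Adding AST is more than an edit, because it alters continued dosing under tier 3. This is correct and is counted as a cost below.

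A character misread from the PDF cannot be wholly excluded. The other inequality signs in Appendix 3 read sensibly, and the sponsor can check quickly.

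**Conclusion.** The sign is wrong as written: nothing in the documents reconciles it with criterion 1 or tier 1. Its effect is that three named tests are optional instead of mandatory for confirmed cases above 35% direct. The ALT-only wording is a secondary misalignment, with Case D as its clearest consequence.

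Severity is minor. The documents give no rate of transaminase rises above 3x ULN, so no count of subjects is claimed. Few are likely, on the judgement that about 100 subjects are planned and exclusion 17 removes ALT or AST at or above 3x ULN at entry. Section 1.1.3 does list raised hepatic enzymes among reactions seen in at least 5% of subjects, without grading, so liver signals are foreseeable.

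The documents do not support an inference that subjects who meet a stopping criterion stay on treatment, or that SAEs go unreported. Section 6.4.5 governs stopping, and Section 11 covers AST.

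**What to change.** First, in the extra work-up line of Appendix 3, change less than 35% direct to more than 35% direct.

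Then align the analyte wording:

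- Tiers 1 and 2 and the extra work-up line: write ALT or AST. In tier 1, add that the SAE status of AST-only cases follows Section 11. Tier 1 declares an SAE unconditionally while Section 11's bilirubin/INR definition requires that no other cause is found, so the clause avoids widening SAE reporting. It does leave ALT and AST treated differently on that one point.
- Tier 3: ALT or AST above 3x ULN, with both below 5x ULN.
- Step-down line: require both ALT and AST below 3x ULN.

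Leave the durations and the 6.4.5 criteria as they are.

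The cost is a protocol amendment, a few more recall visits and liver tests, and three work-up items that become mandatory above 35% direct. Continued dosing for symptom-free AST rises of 3 to 5x also becomes conditional on weekly monitoring for up to 4 weeks. After Day 92 that means 14/7 - 1 = 1 extra test in each 14-day interval and 21/7 - 1 = 2 in the 21-day interval. Sample size and efficacy analyses are unaffected.
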